6.7 Image Processing and Analysis

A trained nuclear medicine physician blinded to results of tissue analysis will evaluate the reconstructed PET, MRI, and fused PET/MR images using a PET volume computer-assisted reading software package. A positive lesion on gallium PSMA-11 PET will be defined as a focus of activity with at least 1.5 times higher SUV compared with mediastinal blood pool that is not attributable to other etiologies of tracer distribution (e.g. excretion) or above liver background. A volume of interest (VOI) will be semiautomatically placed around each lesion, and the calculated maximum standard uptake value (SUV_{max}) will be recorded for each lesion. Adjusted SUV_{max} data will then be averaged across all lesions within a given patient ($SUV_{max-avg}$) if needed. In order to avoid clustering effects, analysis will be limited to the five largest lesions per study.

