6.10 Analyses Plans

The number of ^{68}Ga PSMA-11 PET-positive lesions and number of overall thyroid cancer lesions detected by standard staging scans will be descriptively reported for each patient and correlated with the lesions observed in standard MRI imaging. In addition, the mean, range, and standard deviation of SUV_{max} (across all visualized lesions per patient) and $SUV_{max-avg}$ (across all patients in the study cohort) will be descriptively reported.

For each lesion detected on ^{18}F -FDG PET or radioiodine scintigraphy (^{131}I), the presence or absence of ^{68}Ga -PSMA-11 uptake will be reviewed and tabulated. Presence on either ^{131}I and ^{18}F -FDG will be considered true positive disease. If additional lesions are detected on ^{68}Ga -PSMA-11 as compared to ^{18}F -FDG or ^{131}I , the lesions will be characterized as either true or false positives in comparison to the appearance of the lesion on conventional imaging (thyroid ultrasound, CT and MRI). The gold standard for an individual lesion will be FDG or ^{131}I , if the individual lesion is positive on either imaging study. If the lesions are not seen on either FDG or ^{131}I , then consensus reading of conventional imaging will be performed to determine true and

false positive lesions. The total number of lesions detected using each technique will be compared, and this data will be used to determine the sensitivity and specificity of ^{68}Ga -PSMA-11 for the detection of disease. If a larger number of lesions are detected using ^{68}Ga -PSMA-11 compared to ^{18}F -FDG PET and ^{131}I , this provides promising preliminary data, which can be used to justify study in a larger clinical trial.

The patient cohort will be dichotomized by thyroglobulin level. The mean $\text{SUV}_{\text{max-avg}}$ between dichotomized subgroups will be compared using the non-parametric Mann-Whitney U test. The correlation between SUV_{max} on ^{68}Ga -PSMA PET and thyroglobulin level as a continuous variable will also be determined using Pearson correlation method.

In those patients with adequate archival FFPE the correlation between SUV_{max} on ^{68}Ga -PSMA PET and tumor PSMA expression will be explored using Pearson correlation method.

7 Study Management

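### Section 6.7 caps analysis at the five largest lesions without saying which analyses or whose lesion list, while section 6.10 bases sensitivity on every comparator-detected lesion with no cap

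*Combined protocol and SAP*

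**What the plan says.** Section 6.7 describes the reading of the study scan. A nuclear medicine physician "will evaluate the reconstructed PET, MRI, and fused PET/MR images", a PSMA-positive lesion is defined against blood pool and liver, and "A volume of interest (VOI) will be semiautomatically placed around each lesion" so that SUVmax can be recorded. SUVmax "data will then be averaged across all lesions within a given patient" if needed. The paragraph then closes with the cap: "In order to avoid clustering effects", "analysis will be limited to the five largest lesions per study". FDG and radioiodine are not mentioned in this section, and neither is sensitivity.

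Section 6.10 sets out the sensitivity analysis and does not repeat the cap. "For each lesion detected on" FDG PET or radioiodine scintigraphy, presence or absence of "PSMA-11 uptake will be reviewed and tabulated". A lesion positive on either comparator counts as true disease. Lesions seen on neither are judged by consensus reading of conventional imaging. Sensitivity and specificity come from the total lesions detected by each technique.

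Section 6.8 sizes the study on sensitivity: 0.90 for PSMA against 0.65 for each comparator, one-sided 0.05, power 0.87, 20 patients per comparison.

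**The concern.** The word used in the cap is simply analysis, and its stated reason, clustering, applies to any lesion-level analysis, including sensitivity. Four things are left open: which analyses are capped, which scan supplies the list, how size is measured, and whether a study means a scan or a patient.

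The choice matters because size is plausibly linked to detectability. Keeping the largest lesions drops the small ones that PET is most likely to miss. If the list comes from PSMA-positive volumes, a lesion that PSMA missed is not on it at all.

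Sensitivity is a secondary objective of a feasibility study, but it is the quantity used to size the trial, and section 6.10 intends the lesion counts to support a case for a larger one. As written, the denominator could be settled after the images have been read.

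**Working it through.** **1. The plan's own figure.** Inputs from section 6.8: n = 20, null sensitivity 0.65, alternative 0.90, one-sided 0.05. In an exact one-sample binomial test that succeeds with at least 17 of 20:

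- P(X ≥ 17 | 20, 0.65) = 0.044
- P(X ≥ 17 | 20, 0.90) = 0.867

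This reproduces the stated 0.87. It is a patient-level calculation, and the lesion cap plays no part in it.

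**2. The two denominators.** Take a patient with 8 comparator-detected lesions, of which PSMA shows 5.

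| Reading | Denominator | PSMA sensitivity |
|---|---|---|
| Section 6.10, no cap | 8 | 5/8 = 0.625 |
| Cap, five largest on the reference scan | 5 | depends on whether the missed lesions are the small ones |
| Cap, five largest PSMA-positive lesions | 5 | 5/5 = 1.00 |

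The last row does not need more than five lesions: with 3 seen of 4, 0.75 becomes 3/3 = 1.00.

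**3. Cap applied to a reference-scan list.** The documents give no lesion counts or size gradient, so both are assumed here. Lesions per patient are 1 + Poisson(mean − 1). Standardised log size x is normal. Detection follows logit(p) = a + b·x, with b = 0 (no gradient), 1 or 2 (steep), and a set so that sensitivity over all lesions equals the target. Each setting used 60,000 simulated patients. The table shows sensitivity in the five largest lesions.

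| Mean lesions | Patients with more than 5 | True 0.65: b = 0, 1, 2 | True 0.90: b = 0, 1, 2 |
|---|---|---|---|
| 3 | about 5% | 0.65, 0.66, 0.66 | 0.90, 0.90, 0.90 |
| 5 | about 37% | 0.65, 0.69, 0.71 | 0.90, 0.92, 0.93 |
| 8 | about 83% | 0.65, 0.75, 0.80 | 0.90, 0.94, 0.96 |
| 12 | about 98% | 0.65, 0.81, 0.89 | 0.90, 0.96, 0.985 |

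The bias needs both conditions. It vanishes with no gradient and is negligible when few patients exceed five lesions.

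**4. Separate lists per scan, pooled.** If study means scan, and the five largest from the reference scan are pooled with the five largest from the PSMA scan, a true 0.65 becomes 0.66 at a mean of 3 and about 0.74 at a mean of 12, even with b = 0. The PSMA list adds only positives.

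**5. What a shift would mean for the 17-of-20 rule.** Treat each patient as one success or failure, as section 6.8 does, and suppose selection lifts an apparent 0.65 to a higher value:

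| Apparent sensitivity | P(at least 17 of 20) |
|---|---|
| 0.65 | 0.044 |
| 0.70 | 0.107 |
| 0.75 | 0.225 |
| 0.80 | 0.411 |

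This translation is also an illustration: the plan does not say how lesion results become a patient-level success.

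**The case against.** The strongest reply is that the cap was never meant for sensitivity. It ends a paragraph about volumes of interest and SUVmax, whereas the sensitivity analysis has its own section, which starts from each comparator lesion and uses total counts. The intended use of those counts supports this: with five per scan, any patient with five or more lesions on both scans would score 5 against 5, and extra PSMA lesions could not appear. This is good evidence about intent, and section 6.10 already anchors the tabulation on the comparator. It does not settle the matter, because the cap is unqualified and section 6.10 does not set it aside. The SUV reading is not clean either, since the preceding sentence averages over all lesions in a patient.

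A second reply is that a PSMA-only list is not stated. The reader also evaluates MRI, and a volume goes around each lesion, so a PSMA-negative lesion visible on MRI could be sized and ranked. That stands: the value of 1.00 belongs to one possible reading.

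A third reply is that selecting large lesions may raise comparator sensitivity as well, so a bias in the PSMA-minus-comparator difference has not been shown. That also stands. The figures above concern PSMA sensitivity alone.

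A reader might infer that this trial's sensitivity will be estimated on the easiest lesions and is therefore inflated. The documents do not support that. It would require the cap to govern sensitivity, enough patients with more than five lesions (or a PSMA-derived list), and, for a reference list, better detection of larger lesions. None of these is stated.

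**Conclusion.** The concern holds as an unresolved conflict with a possible bias attached. Sections 6.7 and 6.10 give different lesion denominators, and nothing in the plan says which governs sensitivity. If the cap is applied to it, the size of the upward bias depends on the list:

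- Reference-scan list: for a true 0.65, nil to +0.01 at a mean of 3 lesions and nil to about +0.15 at a mean of 8.
- PSMA-positive list: sensitivity is 1.00 whatever the truth, including in patients with five or fewer lesions.

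The reference-list figures rest on assumed lesion counts and size gradients; the 1.00 follows from the definition of the list. The power statement in section 6.8 is unaffected as arithmetic. Nor does the cap achieve its stated purpose, since up to five lesions from one patient remain correlated.

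**What to change.** In section 6.7, restrict the five-largest rule to SUVmax summaries, name the scan and size measure used for ranking, and align the averaging sentence with it.

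In section 6.10, state that PSMA sensitivity is computed on all lesions of the reference-standard list, compiled without regard to the PSMA result. Lesions that enter only because PSMA showed them and conventional imaging confirmed them should be reported separately, as they are PSMA-positive by definition. Replace the cap as the remedy for clustering with patient-clustered intervals, for example from GEE or a cluster bootstrap over patients.

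The cost is wording in two sections, a numbered lesion list from scans already obtained, and slightly more analysis work. Intervals will be wider and the sensitivity possibly less favourable. No new patients or procedures are needed.

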6.8 Determination of Sample Size and Accrual Rate

Although this is a feasibility study, we will provide a sample size estimate based on the difference in sensitivities between ^{68}Ga -PSMA PET and either ^{131}I and ^{18}F -FDG. To provide an estimate of the needed sample size we assumed that half of the patients will be imaged with ^{131}I and half the patients will be imaged using ^{18}F -FDG PET within 360 days of the ^{68}Ga -PSMA-11 imaging study. We will compare the sensitivity of both ^{131}I and ^{18}F -FDG to ^{68}Ga -PSMA PET. Assuming that both ^{131}I and ^{18}F -FDG have a sensitivity of 0.65 and ^{68}Ga -PSMA PET has a sensitivity of 0.90. Our null hypothesis is that there is no difference between either ^{131}I and ^{18}F -FDG and ^{68}Ga -PSMA PET misclassification rates (H_{null} : ^{131}I / ^{18}F -FDG_misclass = PSMA PET misclass = 65%). The alternative hypothesis is that the FET PET misclassification rate is lower (H_{alt} : PSMA PET misclass < ^{131}I / ^{18}F -FDG_misclass = 65%). Given a power of 0.87, a significance level of 0.05, and a one-sided test, we will require 20 patients for comparison to ^{18}F -FDG and 20 patients for comparison to ^{131}I . This will result in a total sample size of 40. The anticipated accrual rate is approximately 1 to 2 patients per month, leading to an estimated total accrual period of up to 18 to 24 months.

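### Section 6.8 prints a misclassification rate of 65% where its own sensitivities imply 35% and 10%, and its power of 0.87 is not shown for a comparison with a scan measured in the same patients

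*Combined protocol and SAP*

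**What the plan says.** Section 6.8 is the only sample-size justification. It states that 131I and FDG both "have a sensitivity of 0.65 and" that PSMA PET has a sensitivity of 0.90. It then moves to misclassification rates. The null sets the comparator and PSMA rates equal and ends "PSMA PET misclass = 65"%. The alternative gives the comparator rate as 65% again, with no figure for PSMA PET beyond its being lower, and uses a different tracer name: "The alternative hypothesis is that the FET PET misclassification rate is lower". The result is "Given a power of 0.87, a significance level of 0.05, and a one-sided test, we will require 20 patients for comparison to" FDG and another 20 for 131I, 40 in total.

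The comparison is described as one between modalities: "We will compare the sensitivity of both" comparators with PSMA PET. No test is named, and no discordance between the scans is given.

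The analysis text works in lesions. Section 6.7 says: "In order to avoid clustering effects, analysis will be limited to the five largest lesions per study". Section 6.10 says: "The total number of lesions detected using each technique will be compared, and this data will be used to determine the sensitivity and specificity of" PSMA PET, without naming a test for sensitivity. It adds that if PSMA PET finds more lesions, "this provides promising preliminary data, which can be used to justify study in a larger clinical trial".

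Section 3.3.1 requires uptake on FDG PET/CT, I-123 or I-131 scintigraphy for entry. Section 6.10 treats a lesion present on 131I or FDG as true disease. Comparing sensitivity and specificity is the second secondary objective in section 2.2.

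**The concern.** Two things in section 6.8 do not fit together.

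First, 65% is the comparators' sensitivity, yet it appears as their misclassification rate. A reader who takes the hypotheses as printed cannot recover the stated power.

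Second, the text describes a comparison with scans read in the study's own patients, whereas the stated power looks like that of a test against a known constant. A measured comparator carries sampling error, and the power of a paired comparison depends on how often the two scans disagree in each direction. The plan gives nothing on this.

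At stake is how the sample-size statement and the second secondary objective are read. A reader could take it that each comparison of modalities has 87% power. Section 6.10 says a favourable lesion count can be used to support a larger trial, so the basis of the figure should be clear.

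**Working it through.** **Inputs from section 6.8.** Comparator sensitivity 0.65; PSMA PET sensitivity 0.90; one-sided level 0.05; n = 20 per comparator; stated power 0.87; printed misclassification 65%.

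**Step 1. Convert sensitivity to misclassification of disease.** 1 − 0.65 = 0.35 for the comparators; 1 − 0.90 = 0.10 for PSMA PET under the alternative. Neither is 65%.

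**Step 2. Reproduce 0.87.** Let X be the number of 20 patients positive on PSMA PET, X ~ Bin(20, p).
- Rejecting at X ≥ 17: P(X ≥ 17 | p = 0.65) = 0.0444; P(X ≥ 17 | p = 0.90) = 0.8670.
- Rejecting at X ≥ 16 would give size 0.118, so 17 is the cut-off.
- On the misclassification scale this is the same test: reject at 3 or fewer missed, 0.35 against 0.10.

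The uncorrected one-sample normal approximation also gives 0.867. Two independent groups of 20 give 0.60 (one-sided normal approximation) or 0.48 (Fisher exact). The one-sample reading is therefore an inference, but the match is close.

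**Step 3. Use the printed null.** Let Y be the number misclassified. With a null of 0.65, P(Y ≤ 8) = 0.0196 and P(Y ≤ 9) = 0.0532, so the test rejects at Y ≤ 8. At the implied 0.10, power is P(Y ≤ 8 | 0.10) = 0.9999. The 10% is derived from the stated 0.90, not printed.

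**Step 4. Compare with a scan measured in the same 20 patients.** Let c = P(comparator+, PSMA−) and b = P(PSMA+, comparator−). The sensitivities fix b − c = 0.90 − 0.65 = 0.25. The documents do not give c. It cannot be below 0, or above 0.10 (all that PSMA PET misses), so total discordance runs from 0.25 to 0.45. McNemar power, one-sided 0.05, n = 20, by full enumeration over the number of discordant pairs:

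| c (assumed) | Discordance | Exact | Mid-p | Uncorrected asymptotic |
|---|---|---|---|---|
| 0 | 0.25 | 0.59 | 0.77 | 0.91 |
| 0.025 | 0.30 | 0.51 | 0.67 | 0.73 |
| 0.065 (independent errors: 0.65 × 0.10) | 0.38 | 0.42 | 0.55 | 0.60 |
| 0.10 | 0.45 | 0.37 | 0.49 | 0.54 |

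The first row can be checked by hand. With c = 0, every discordant pair favours PSMA PET and their number D is Bin(20, 0.25). The exact test needs D ≥ 5 (0.5^5 = 0.031, whereas 0.5^4 = 0.0625), with probability 0.585. Mid-p needs D ≥ 4, with probability 0.775. The asymptotic test needs D ≥ 3 (√3 = 1.73 > 1.645), with probability 0.909.

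**Step 5. Unit of analysis.** Steps 2 to 4 count patients, as section 6.8 does; section 6.10 counts lesions. Lesion-level power also needs the number of lesions per patient and the within-patient correlation. Neither is given, so it cannot be computed from the documents and could lie on either side of 0.87.

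**Step 6. The 0.65 at patient level.** If a patient's qualifying scan under section 3.3.1 is also the comparator, that patient enters with comparator uptake, and section 6.10 counts a comparator-positive lesion as true disease. Among such patients comparator sensitivity is 1 by construction, so 0.65 could not be observed.

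**The case against.** The strongest reply is that this is a feasibility study, which section 6.8 says at the outset. Section 6.10 specifies no significance test for sensitivity, and n = 20 survives the relabelling. Section 6.8 also gives the comparator one fixed value in both hypotheses, which suits a benchmark test, and on that reading 0.87 is correct. All of this stands, and it limits the consequence. It does not rescue the printed 65%, and the same section still describes a comparison of modalities.

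One might try to save the printed figure by reading it as 65% against 35% misclassification. That gives power 0.878 when rejecting at 9 or fewer, but the size is then 0.053, and 35% contradicts the stated PSMA PET sensitivity of 0.90.

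Some stronger readings should also be set aside:
- **The plan ignores clustering.** Section 6.7 addresses it with a cap of five lesions per study. The cap limits clustering without removing it, and whether it governs the section 6.10 lesion comparison is not explicit.
- **The 0.65 can only describe lesions.** That does not follow. Section 3.3.1 allows several qualifying scans, so the qualifying scan need not be the comparator; 0.65 may also be only a planning benchmark.
- **Section 6.10 commits to a larger trial on a favourable count.** It says only that the data can be used to justify one.

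**Conclusion.** The point holds as a reporting error together with a power claim not shown for the comparison described.

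The label error needs no outside assumption: 65% is printed where 35% and 10% are implied, and the alternative names the wrong tracer. That 0.87 is one-sample power is inferred from the numerical match, because no test is named.

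For a paired patient-level comparison, the figures assume sensitivities of 0.65 and 0.90, independent patients, and c between 0 and 0.10. Exact and mid-p power stay below 0.87 across that range. The uncorrected asymptotic test exceeds it only near c = 0, where PSMA PET misses almost nothing that the comparator finds; at c = 0.025 it is already 0.73.

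A reader might infer that 87% power is impossible, or that 40 patients are too few. The documents support neither: discordance, the test and the lesion-level inputs are not given, and the primary feasibility objective does not rest on this calculation. This should be fixed, but it affects only the sample-size statement and the reading of the second secondary objective.

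**What to change.** In section 6.8:
- Change the misclassification rate from 65% to 35% in both hypotheses, state 10% for PSMA PET under the alternative, and replace FET PET with PSMA PET.
- State that 0.87 is the power of a one-sample, one-sided test against a fixed 65% sensitivity benchmark, and that it is not shown for a paired comparison with either measured scan.
- Add a sentence noting that a patient-level comparator sensitivity of 0.65 cannot be observed in patients whose qualifying scan is also the comparator.

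In section 6.10, choose one:
- Keep the comparison of modalities descriptive, with confidence intervals. As a guide to precision, 18 of 20 gives an exact 95% CI of 0.68 to 0.99.
- Name a paired test and its unit, and restate its power with the assumed discordance. If lesions are the unit, also state the assumed number per patient and within-patient correlation.

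The cost is a few sentences. No patients or procedures are added; the only downside is a less favourable power statement.

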6.9 Interim Analyses and Stopping Rules

After each patient is imaged, the acquired data will be reviewed to determine the optimal image acquisition. If ^{68}Ga -PSMA uptake is not appreciated in any of the first five patients imaged, study accrual will be halted and the imaging protocol will be re-evaluated. A sample size of five patients for interim analysis will allow for a preliminary analysis of image quality and ability of ^{68}Ga -PSMA PET to detect thyroid cancer metastases.

6.10 Analyses Plans

The number of ^{68}Ga PSMA-11 PET-positive lesions and number of overall thyroid cancer lesions detected by standard staging scans will be descriptively reported for each patient and correlated with the lesions observed in standard MRI imaging. In addition, the mean, range, and standard deviation of SUV_{max} (across all visualized lesions per patient) and $SUV_{max-avg}$ (across all patients in the study cohort) will be descriptively reported.

For each lesion detected on ^{18}F -FDG PET or radioiodine scintigraphy (^{131}I), the presence or absence of ^{68}Ga -PSMA-11 uptake will be reviewed and tabulated. Presence on either ^{131}I and ^{18}F -FDG will be considered true positive disease. If additional lesions are detected on ^{68}Ga -PSMA-11 as compared to ^{18}F -FDG or ^{131}I , the lesions will be characterized as either true or false positives in comparison to the appearance of the lesion on conventional imaging (thyroid ultrasound, CT and MRI). The gold standard for an individual lesion will be FDG or ^{131}I , if the individual lesion is positive on either imaging study. If the lesions are not seen on either FDG or ^{131}I , then consensus reading of conventional imaging will be performed to determine true and

false positive lesions. The total number of lesions detected using each technique will be compared, and this data will be used to determine the sensitivity and specificity of ^{68}Ga -PSMA-11 for the detection of disease. If a larger number of lesions are detected using ^{68}Ga -PSMA-11 compared to ^{18}F -FDG PET and ^{131}I , this provides promising preliminary data, which can be used to justify study in a larger clinical trial.

The patient cohort will be dichotomized by thyroglobulin level. The mean $\text{SUV}_{\text{max-avg}}$ between dichotomized subgroups will be compared using the non-parametric Mann-Whitney U test. The correlation between SUV_{max} on ^{68}Ga -PSMA PET and thyroglobulin level as a continuous variable will also be determined using Pearson correlation method.

In those patients with adequate archival FFPE the correlation between SUV_{max} on ^{68}Ga -PSMA PET and tumor PSMA expression will be explored using Pearson correlation method.

7 Study Management

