3.3.1 Inclusion Criteria

1. History of thyroid cancer
2. Whole body ^{18}F -FDG PET/CT, I-123 or I-131 scintigraphy within the past 360 days of the scheduled ^{68}Ga -PSMA PET demonstrating uptake.
3. Age 18 years or older at the time of study entry
4. Creatinine $\leq 3.0 \text{ mg/dL}$
5. Ability to understand a written informed consent document, and the willingness to sign it

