5.1.1 Screening Assessments

The Screening procedures and assessments must be completed within 28 days of the Day 1 Visit, unless otherwise noted.

A written, signed, informed consent form (ICF) and a Health Insurance Portability and Accountability Act (HIPAA) authorization must be obtained before any study-specific assessments are initiated. A copy of the signed ICF will be given to the subject and a copy will be filed in the medical record. The original will be kept on file with the study records.

All patients who are consented will be registered in OnCore®, the UCSF Helen Diller Family Comprehensive Cancer Center Clinical Trial Management System (CTMS). The system is password protected and meets HIPAA requirements.

In addition to OnCore, REDCap will be used to collect data for this study. REDCap is a secure, HIPAA-compliant, web-based system.

- Complete medical history
- Baseline standard staging diagnostic exams may be done approximately 360 days before PSMA PET as clinically indicated. Patients may receive staging scans and ⁶⁸Ga-PSMA PET imaging on the same day if the patient meets eligibility criteria for the study as assessed by the Principal Investigator prior to the completion of the scan.
- Pregnancy testing in women of childbearing potential (WOCBP)
- Creatinine
- Thyroglobulin

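### Section 6.10 counts a lesion seen on a comparator scan up to 360 days old as current disease, so a lesion surgically removed before PSMA PET is in effect scored as a PSMA miss.

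*Combined protocol and SAP*

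**What the plan says.** Section 6.10 tabulates PSMA uptake as present or absent for each lesion detected on FDG PET or radioiodine scintigraphy. Presence on either comparator "will be considered true positive disease", and that scan is the gold standard for the lesion "if the individual lesion is positive on either imaging study". Conventional imaging is used as a reference only for lesions seen on neither comparator: there, "consensus reading of conventional imaging will be performed to determine true and" false-positive lesions. The same section uses these data for sensitivity and specificity. It describes a larger PSMA lesion count as promising preliminary data, "which can be used to justify study in a larger clinical trial".

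On timing, inclusion criterion 2 in Section 3.3.1 accepts FDG PET/CT, "I-123 or I-131 scintigraphy within the past 360 days of the scheduled" PSMA PET. Footnote 1 to the schedule table in Section 5.1.4 gives the same limit and also permits same-day scans. Sections 3.3.1 and 3.3.2 place no limit on treatment between the two scans.

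Three other provisions bear on the point:

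- Section 6.7 states that "analysis will be limited to the five largest lesions per study".
- Section 6.10 says that lesion counts are "correlated with the lesions observed in standard MRI imaging".
- Section 5.1.1 lists "Complete medical history" at screening, and the schedule table adds prior and concomitant systemic therapies.

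**The concern.** Section 6.10 treats the comparator scan as a statement about disease on the day of PSMA PET, but that scan may be almost a year old. Section 1.1 names surgery, radioiodine, external beam radiation and kinase inhibitors as treatments for this disease, so a lesion can be treated between the scans. The protocol itself expects change over a shorter period: the optional repeat scan in Section 5.1.4, at 2 to 6 months, looks for interval change in PSMA uptake.

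A lesion resected in the interval cannot take up the tracer. Under the stated rule it remains reference-positive and is recorded as PSMA-absent. The miss comes from the surgery and the scan interval, not from the tracer. Comparing the sensitivity of PSMA PET with FDG and radioiodine is secondary objective 2 in Section 2.2, and Section 6.8 builds the sample size on that comparison.

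**Working it through.** **1. Does any provision correct the scoring?**

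- The consensus read does not, because it applies only to lesions negative on both comparators.
- The MRI correlation is descriptive and rescores no lesion. Sections 5.1 and 5.1.2.1 give the MRI acquired with PSMA PET the roles of attenuation correction and localization.
- The five-lesion limit restricts which lesions are analysed, not whether they still exist.
- Treatment history is collected, but no rule connects it to a lesion's score.

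The gap is therefore in the scoring rule rather than clearly in the data.

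**2. The plan's own figure.** Section 6.8 gives sensitivities of 0.65 and 0.90, a one-sided 0.05 level, 20 patients per comparison and power 0.87. An exact binomial test of 20 patients against 0.65 rejects at 17 or more positives. Its size is 0.044 and its power at 0.90 is 0.867, so the stated figure reproduces. It is not in dispute.

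**3. Inputs for the illustration.** From Section 6.8, comparator sensitivity is C = 0.65 and PSMA sensitivity is P = 0.90. Let f be the share of comparator-positive lesions removed before PSMA PET. The documents give no value for f; 0, 5% and 10% are assumptions. Removed lesions are taken to show no uptake.

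**4. Comparator-positive lesions as denominator.** Apparent PSMA sensitivity = P(1 − f):

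- f = 0: 0.90
- f = 5%: 0.90 × 0.95 = 0.855
- f = 10%: 0.90 × 0.90 = 0.81

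**5. All confirmed lesions as denominator.** Assume further that the tracers detect lesions independently given disease, that every true PSMA-only lesion is confirmed, and that comparator-negative lesions persist. As shares of all true lesions:

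- seen on both scans: 0.65 × 0.90 = 0.585
- PSMA only: 0.35 × 0.90 = 0.315
- all confirmed: 0.65 + 0.315 = 0.965

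Apparent PSMA sensitivity = [0.585(1 − f) + 0.315] / 0.965:

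- f = 0: 0.900 / 0.965 = 0.933
- f = 5%: 0.87075 / 0.965 = 0.902
- f = 10%: 0.8415 / 0.965 = 0.872

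**6. Effect of leaving removed lesions out of the PSMA denominator.**

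- Comparator-positive lesions: 0.585(1 − f) / [0.65(1 − f)] = 0.90 for any f.
- All confirmed lesions: 0.87075 / 0.9325 = 0.934 at 5% and 0.8415 / 0.900 = 0.935 at 10%, against 0.933 with no removal.

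**7. Should the same exclusion apply to the lesion count?** Let g be lesions that arise in the interval, as a share of original lesions (also not in the documents). Assume that PSMA PET detects 0.90 of them. The PSMA-to-comparator count ratio is [0.585(1 − f) + 0.315 + 0.90g] / 0.65. Excluding removed lesions changes the divisor to 0.65(1 − f).

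| f = g | Rule as written | Removed lesions excluded |
|---|---|---|
| 0 | 0.900 / 0.65 = 1.385 | 1.385 |
| 5% | 0.91575 / 0.65 = 1.409 | 0.91575 / 0.6175 = 1.483 |
| 10% | 0.9315 / 0.65 = 1.433 | 0.9315 / 0.585 = 1.592 |

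In the count, removed and new lesions partly offset. Excluding only the removed ones moves the ratio further from 1.385, in favour of PSMA. The exclusion therefore suits the sensitivity denominator but not the count.

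**The case against.** The strongest reply is that this is a single-center pilot whose primary objective is feasibility and utility, with sensitivity secondary. Treatment history is collected, and PET, MRI and fused images are read together, so a reader could recognise a resected site. Section 6.10 never uses the term false negative, and same-day scans remove the problem. All of this is correct, and it limits the weight of the point. It does not remove it: recognising a resected site changes nothing when no rule permits rescoring, and a reference-positive lesion recorded without uptake can only count against PSMA sensitivity.

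A reader might infer a loss of power. Putting 0.855 and 0.81 into the 20-patient test would give 0.67 and 0.46 instead of 0.867. The documents do not support that step. Section 6.8 counts patients, Section 6.10 counts lesions and names no test for sensitivity, and a patient who loses one of several lesions need not become PSMA-negative. The result also depends on the denominator. The comparator's sensitivity among comparator-positive lesions is 1 by construction, so 0.65 is not a coherent benchmark there. With the all-confirmed values 0.902 and 0.872, the same test would give 0.875 and 0.752. No power figure is claimed.

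A reader might also infer that a decision to proceed is compromised. Section 6.10 offers a larger PSMA count only as preliminary support for a larger trial and sets no threshold.

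**Conclusion.** The point holds for PSMA sensitivity. Read as written, Section 6.10 scores a lesion removed between the scans as a PSMA miss, and nothing elsewhere in the plan corrects this. The bias is downward. Its size cannot be determined, because f is not given: it is zero for same-day scans and for patients with no lesion removed. At an assumed f of 5% or 10%, the fall is 0.045 or 0.09 on comparator-positive lesions (0.90 − 0.855; 0.90 − 0.81). On all confirmed lesions it is about 0.03 or 0.06 (0.933 − 0.902; 0.933 − 0.872). The second pair also rests on conditional independence and full confirmation of PSMA-only lesions.

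The point applies only within the analysed set of lesions and does not touch the feasibility aim. It should be corrected in the analysis plan, but it is not a reason to alter eligibility or imaging.

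**What to change.** In Section 6.10:

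1. Record both scan dates and all interval therapy, local and systemic, from the chart. Report the scan interval.
2. Before PSMA results are consulted, identify the comparator-positive lesions documented as surgically removed between the scans. Leave them out of the PSMA sensitivity denominator only, and tabulate them separately. Fixing the list in advance prevents selective removal of misses.
3. Keep lesions treated in other ways in the main analysis. Add a sensitivity analysis of sensitivity and lesion counts limited to patients with no interval treatment.
4. Leave the main lesion-count comparison unchanged, for the reason in step 7 of the working. Describe PSMA-only lesions by scan interval.

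The cost is plan wording and a few chart fields, with no new imaging. The PSMA denominator becomes slightly smaller and no longer matches the comparator's exactly, so both should be shown. The untreated-patient analysis will be imprecise, since each comparison has only 20 planned patients. Lesions eliminated without surgery stay in the main analysis, so some bias remains there.
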